**Figure 2. PrEP4Her Implementation Science Research Logic Model**

**Figure Legend.** Causal pathways between implementation strategies, mechanisms and outcomes are designated with superscripts.

**Community advisory board (CAB):** Throughout the study to promote researcher-community collaboration, we will convene a CAB of 6-8 individuals (not including involvement by [name] as researcher representation) – including Black cis-gender women and gynecology practitioners. To ensure we obtain adequate feedback from community members, we will have at least half of our CAB be Black cis-gender women: aged 18-45, self-reported HIV negative, sexually active in the last 6 months and not in a monogamous relationship (to reflect potentially PrEP eligible women). We will recruit CAB members from prior research studies with Black cis-gender women and solicit referrals from the University of Alabama at Birmingham Center for Women's Reproductive Health as well as the AL American College of Obstetricians and Gynecologists (see Letters of Support). In Aim 1, the CAB will meet monthly (following a kick-off meeting) to get initial feedback on our interview guide and help us to

interpret our qualitative findings. In Aim 2, the CAB will meet bi-weekly for 3 months to engage in the process of selecting and refining components of our implementation strategy (PrEP4Her). In Aim 3, the CAB will advise on how to disseminate study results and will resume monthly meetings. We expect at least 10 meetings, during the study and we will adopt a shared decision making structure and take detailed notes to evaluate meeting processes. CAB members will receive a \$10 stipend per meeting.

**Specific Aim1. Evaluate key individual-, inner-setting, and process-level determinants for implementation of PrEP service delivery in gynecology clinic settings using concurrent mixed-methods study design. Concurrent Mixed-methods Research Design:** Quantitative and qualitative data will be collected concurrently and integrated using transformation integration procedures (i.e. quantifying themes and/or codes from qualitative data and incorporating it into quantitative databases), to determine major barriers and facilitators to implementing PrEP into gynecology care and, further aid in development and refining of components to include in PrEP4Her in Aim 2.

**Sub-aim 1:** Assess process and inner-setting determinants conducted with key-informants to explore perceived barriers and facilitators for integrating PrEP into routine gynecological clinical care.

**Qualitative Study Design:** Key informant in-depth interviews will be conducted with gynecologists, practice managers, medical assistants, nurses and pharmacists at our clinical site.

**Sample:** Open-ended qualitative interviews will be conducted with 15-20 key informants currently employed at our GYN clinical site.

**Procedures and Qualitative Data Analysis.** These

interviews will provide contextual information on barriers to PrEP implementation, which will influence design of our implementation

strategy. **(Table. 1)** Potential Interview guide) Also, based on analyses from Aim 1, potential key determinants for intervention development will be vetted during these interviews to assess feasibility of intervention implementation.

Medical service providers will include nurse practitioners, gynecologists and internist who provide women's healthcare. We will also engage with case managers and social workers to discuss coverage for PrEP services and programs that exist for those not insured. Digital audio-recorders will be used to record all key informant interviews. Interviews will be conducted via teleconference.

**Data Analysis:** [name] will lead coding and analytic approach; she has extensive experience conducting qualitative research and working with analytic teams. Analytic steps will include: 1) After each interview, interviewers will document field notes including emerging topic areas for subsequent exploration. 2) After interviews have been completed and recordings transcribed, transcripts will be uploaded to an encrypted password protected computer and NVivo qualitative data management software (QSR International, Melbourne, Australia) will be used to organize coding and analysis. 3) A preliminary codebook will be developed to include inductive codes that emerge from data (e.g. barriers to PrEP implementation, suggested workflow models, etc.) and pattern codes that connect concepts to one another. 4) The coding team will apply codes to a subset of transcripts in parallel, comparing coding strategies and adjusting code definitions until adequate inter-coder reliability is achieved. 5) As the team is applying codes, they will also continuously develop analytic memos reflecting dimensions and characteristics of each code, as well as noting major themes. 6) Data matrices will be created to visually represent relationships between key concepts and elicit patterns in the data. Throughout this process, the qualitative team will hold weekly analysis meetings.

**Quantitative Study Design:** Cross-sectional study will be done in collaboration with the AL American College of Obstetricians and Gynecologists and the UAB Center for Women's Reproductive Health in the Department of Obstetrics and Gynecology (letters of support provided) to understand barriers to future state-wide implementation that would need to be measured during this study pilot.

**Table 1. Potential Qualitative Interview Topics**

Topics (will inform PrEP4Her)	Operationalized Topics
Key-informant Interviews (N = 20)	
Factors effecting PrEP implementation at GYN Clinics	
 
For GYN providers, what are the major barriers and facilitators when caring for patient's sexual health?
 

Key barriers/facilitators to implementation	
 
What would be the major determinants that influence implementing PrEP services into GYN routine care?
 

Potential strategies to address barriers	
 
What strategies would help overcome barriers?
 

Black Cis-gender Women Focus Groups (N = 30)	
Sexual Health	
 
How do you prefer to communicate with your healthcare team about sexual health?
 
Who would you feel most comfortable communicating with?
 
What type of information would be preferred when discussing?:
 
HIV and PrEP
 
 
 
What information would be needed to feel comfortable speaking to a provider about PrEP and HIV prevention?
 
What information would help decrease stigmatizing beliefs about HIV and PrEP?
 
What would ideal communication between your healthcare team about PrEP look?
 

Education needed to increase awareness and knowledge	
Stigma	
Communication with care team	

**Sample:** Participants (N = 250) will be recruited from the state of Alabama. *Inclusion criteria:* 1) currently practicing gynecologists or advanced practitioners at GYN clinics 2) English speaking, 3) Age  $\geq 18$ .

**Methods:** Survey will evaluate structural barriers to PrEP, as well as incorporate potential provider-level barriers.

**Data Management:** REDCap (Research Electronic Data Capture) will be used for electronic surveys and is a secure, Web-based application designed to support data capture for research studies.

**Data collection:** Gynecologists will be recruited through direct referral (from AL ACOG and UAB OB/GYN Center for Research) either through email correspondence or direct communication. A prescreening electronic query that will identify whether they meet inclusion criteria will be given through email correspondence, followed by consent. Data will be collected using a secure electronic server and will be designed to only last approximately 15 minutes. Surveys will include sociodemographic variables and validated scales to determine HIV/PrEP knowledge, HIV/PrEP stigma as well as questions to ascertain current routine testing and screening practices.

**Power Calculations and sample size considerations:** We will administer our survey to 250 Alabama gynecologists. This sample size will allow us to detect odds ratios of willingness to prescribe PrEP of 2.09 for binary variables (50% in each group across study) and 1.47 for a standard deviation change in continuous variables assuming 80% power, 30% baseline percentage of willingness to prescribe PrEP, no other variables in the model, and Type 1 error rate of 5%. When covariates are included that have a correlation of 0.2 with the independent variable, the detectable ORs increase (2.27 and 1.54 respectively for binary and continuous variables).

**Primary outcome:** Willingness to prescribe PrEP (categorical, yes vs no).

**Secondary outcome:** Belief clinical-setting capable of providing PrEP services (ordinal, 1-10)

**Independent variables:** Expected variables as listed in *Table 2*.

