**Table 2. Expected Independent Variables, RE-AIM Constructs**

Independent Predictor Variable	RE-AIM Construct	Measures
Clinical-setting level - Determine denominator (i.e. number of providers in clinical settings) willing to prescribe PrEP and factors associated with their willingness - Determine belief current clinical setting prepared to provide PrEP services	Adoption	- Socio-demographics: race/ethnicity, clinic name, gender, years of practice, clinic resources, characteristics of populations served - Knowledge: PrEP and HIV - Stigma: PrEP and HIV - Practice: Sexual history, STI testing, STI treatment

**Descriptive statistics:** Frequencies for reported willingness to prescribe PrEP will be reported overall and for each independent variable. Descriptive statistics (median/interquartile ranges, frequencies/percentages) and comparisons between those willing to prescribe PrEP and not willing will be reported for each independent variable in bivariate logistic regressions. Multivariable logistic regression models will be performed adjusting each independent variable by a priori variables, such as age, race and sex, and other variables included based on literature review.

**Logistic regression analyses:** Bivariate models will be fit and variables with p-values  $\leq 0.1$  will be included in multivariable logistic regression analyses. Model fit will be determined using Hosmer and Lemeshow tests. A priori variables will be selected and included based on literature review.

**Sub-aim 2:** To further assess individual-level determinants, we will conduct focus groups with Black cis-gender women living in Alabama to explore desired PrEP educational materials and communication strategies from gynecologic care teams.

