**Procedures.** Potential participants who are referred will be asked to complete an online screening tool to determine whether they meet eligibility criteria and to collect demographic data. If participants are eligible, study staff will contact them via phone to schedule focus groups. Focus groups will be conducted in private, quiet, mutually convenient locations by study staff who are trained in qualitative methods and interview techniques. Informed consent will be obtained prior to each focus group and participants will receive \$50 in compensation upon completion. All focus groups will be digitally audio recorded, professionally transcribed, and de-identified.

**Qualitative Data Analysis.** See Qualitative analyses sub-Aim 1.

**Data Integration:** We will be integrating our qualitative and quantitative data findings through joint displays, bridging results using visual displays to connect major themes.

**Expected Outcomes:** Following evaluation of overall themes, findings from this aim will create an in-depth and granular understanding of key factors that are necessary to address in development and refinement of PrEP4Her, our implementation strategy to integrate PrEP services into routine GYN care. Large sampling of GYN providers will also allow for greater generalizability of our implementation strategy to other Southern sites.

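### The provider survey reports a willing-to-prescribe share from a referral sample with no stated frame or invited count, and gives no recruitment route for the eligible advanced practitioners

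*Combined protocol and SAP*

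**What the plan says.** All of this is in the protocol under Specific Aim 1, Sub-aim 1, unless noted.

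- **Purpose.** Quantitative Study Design says the survey is to identify barriers to later state-wide implementation. Willingness to prescribe (yes or no) is the primary outcome, and Descriptive statistics reports its frequency overall. Table 2 places it under the Adoption construct: "Determine denominator (i.e. number of providers in clinical settings) willing to prescribe PrEP", together with factors associated with willingness.
- **Eligibility and size.** Sample admits "currently practicing gynecologists or advanced practitioners at GYN clinics" and states: "Participants (N = 250) will be recruited from the state of Alabama".
- **Recruitment.** Data collection says: "Gynecologists will be recruited through direct referral (from AL ACOG and UAB OB/GYN Center for Research) either through email correspondence or direct communication". It continues: "A prescreening electronic query that will identify whether they meet inclusion criteria will be given through email correspondence, followed by consent".
- **Power.** The power section says: "We will administer our survey to 250 Alabama gynecologists". The size is justified by the ability to "detect odds ratios of willingness to prescribe PrEP of 2.09 for binary variables (50% in each group across study) and 1.47" per standard deviation of a continuous variable.
- **Generalization.** Expected Outcomes for Aim 1 states: "Large sampling of GYN providers will also allow for greater generalizability of our implementation strategy to other Southern sites".
- **Acknowledged bias.** Section C4 discusses selection bias for the Black cis-gender women who take part, not for the surveyed providers.

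The PrEP4Her Analysis Plan covers Aim 3 and adds nothing on this survey.

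**The concern.** A percentage willing, read at state level, is only as good as the route by which respondents arrived. Providers referred by a professional college or a university department, who then choose to answer a PrEP survey, may differ in willingness from those who are not referred or do not answer. Section C4 makes this argument for the women: those interested may hold less stigma. It is not carried over to the providers.

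Without a frame or an invited count there is no response rate, so a reader cannot bound the possible error. Expected Outcomes rests generalizability on a large sample, but size shrinks sampling error and leaves selection error where it was.

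The second strand is coverage. Two professions are eligible, yet the recruitment and power text names one. Followed literally, it recruits only referred gynecologists. Because Table 2 lists no provider-type variable, the mix of respondents could not be checked afterwards.

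At stake are the reported share and the generalizability statement. The planned odds ratios are less exposed: if participation depends on willingness alone, they are not distorted. They would be distorted if it depended jointly on willingness and a predictor such as stigma or knowledge.

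**Working it through.** **1. The plan's own figure.** Inputs from the power section: N = 250, split 125/125, 30% baseline, 80% power, 5% type 1 error (taken as two-sided).

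- Binary: baseline odds 0.30/0.70 = 0.4286; times 2.09 = 0.8957; second proportion 0.8957/1.8957 = 0.4725. The pooled two-proportion test without continuity correction needs N = 248 and has 80.4% power at N = 250.
- Continuous: OR = exp[(1.960 + 0.842)/√(250 × 0.30 × 0.70)] = exp(2.802/7.246) = 1.47.

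Both unadjusted figures reproduce. They concern associations and say nothing about the accuracy of the share.

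**2. Sampling error of the share.** The plan states no precision for it. Taking 30% as the share and 250 completed surveys: 1.96 × √(0.30 × 0.70/250) = 0.057, a 95% interval of 24.3% to 35.7%.

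**3. Selection.** Let k be participation of willing relative to unwilling providers. Observed share = 0.30k/(0.30k + 0.70). The documents give no k, so these values are assumptions on both sides of 1.

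| k | Calculation | Observed | Shift (points) |
|---|---|---|---|
| 0.67 | 0.201/0.901 | 22.3% | −7.7 |
| 1 | 0.300/1.000 | 30.0% | 0 |
| 1.25 | 0.375/1.075 | 34.9% | +4.9 |
| 1.5 | 0.450/1.150 | 39.1% | +9.1 |
| 2 | 0.600/1.300 | 46.2% | +16.2 |

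The shift is inside the 5.7-point half-width at k = 1.25 and outside it at 0.67, 1.5 and 2. N does not appear in the formula.

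**4. What an invited count would allow.** With 250 completed and 75 willing, the worst-case bounds are 75/invited and (75 + invited − 250)/invited. Response rates are assumed.

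| Response | Invited | Bounds |
|---|---|---|
| 90% | 278 | 27% to 37% |
| 70% | 357 | 21% to 51% |
| 50% | 500 | 15% to 65% |
| 30% | 833 | 9% to 79% |

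**5. Missing advanced practitioners.** If none were reached, the error in the share is −(their fraction of providers) × (their willingness minus gynecologists'). Assuming a fraction of 10% to 50% and a difference of −10 to +20 points, the error runs from 0.10 × 10 = 1 point to 0.50 × 20 = 10 points in size, and its direction depends on the sign of the difference.

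**6. What 250 counts.** Sample speaks of recruiting 250 and the power section of administering the survey to 250. If 250 is the number approached, 70% response gives n = 175, with 65% power at OR 2.09 and a detectable OR of 2.39. At 50%, n = 125, power is 51% and the detectable OR is 2.80.

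**The case against.** The strongest reply is that nothing here shows the share to be wrong. There are no response data, every ratio above is assumed, and a mild one (1.25) moves the share by less than the sampling half-width. A ratio below 1 lowers it. This stands: a reader might infer that the share is biased, and biased upward, but the documents support only a risk of unknown size and direction.

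Similarly, a reader might infer that advanced practitioners are under-covered. They are eligible, the pre-screen applies the inclusion criteria, the word gynecologists may be shorthand, and referral could reach them. What is shown is a mismatch between sections and no means of checking coverage.

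A third tempting reading is that the trial's Adoption result is compromised. It is not. Under Aim 3 and in Paper 1 of the Analysis Plan, Adoption is the proportion of pilot-site stakeholders willing to initiate the strategy, measured by training attendance, website clicks, a survey item and chart review. None of these uses the survey share, despite Table 2's label.

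It can also be said that the survey is formative and powered for odds ratios, that Expected Outcomes claims generalizability for the strategy and not for the percentage, and that e-mail through the college may in practice reach its full list. The first two limit the seriousness. They do not rescue the reasoning that a large sample confers generalizability. The third is possible but unstated.

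Finally, recruitment has probably closed: Aim 1 feeds the pilot, whose dates run to August 2024, and the Analysis Plan was started in September 2025. Survey status is not reported. This changes which remedies remain open, not the point itself.

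**Conclusion.** The point holds as a risk to one descriptive result and one sentence of interpretation. The willing share comes from a referral sample with no stated frame, invited count or response rate, so its closeness to the state-wide figure cannot be judged. Under assumed participation ratios of 0.67 to 2, a true 30% would appear as anything from about 22% to 46%, against 5.7 points of sampling error either way. These are illustrations, and they take the power section's 30% baseline as the true overall share, which the plan does not assert.

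Advanced practitioners are eligible without a stated recruitment route, sample size or identifying variable. The odds ratios and the pilot-site Adoption measure are not the main concern. The absence of a frame or count is judged on the available public text. This is worth correcting because the remedy is cheap and the survey is meant to inform state-wide implementation.

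**What to change.** If the survey is still open:

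- Reconcile Sample with Data collection and the power section on who is surveyed.
- Send the invitation to the college's full Alabama list and to an equivalent list of advanced practitioners.
- Record provider type and referral source for each respondent.
- Log invited and completed counts, and state which of them 250 means.

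In the analysis and report, whether open or closed:

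- Give response rates by profession and source.
- Show the willing share with and without respondents from the collaborating university department. Clinic name is already collected and may make this possible.
- If a non-response bound is given, make it two-sided. Counting every non-responder as unwilling is only one extreme.
- Confine the generalizability sentence in Expected Outcomes to the providers who responded, and add provider selection to section C4.

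If the survey has closed, reconstruct the counts from invitation and referral records, or state that no response rate can be calculated, and report profession and source where they were recorded.

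The cost is a little more administration and a few table rows. The downside is a wider, more qualified willingness figure.

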**Table 2. Expected Independent Variables, RE-AIM Constructs**

Independent Predictor Variable	RE-AIM Construct	Measures
Clinical-setting level - Determine denominator (i.e. number of providers in clinical settings) willing to prescribe PrEP and factors associated with their willingness - Determine belief current clinical setting prepared to provide PrEP services	Adoption	- Socio-demographics: race/ethnicity, clinic name, gender, years of practice, clinic resources, characteristics of populations served - Knowledge: PrEP and HIV - Stigma: PrEP and HIV - Practice: Sexual history, STI testing, STI treatment

**Descriptive statistics:** Frequencies for reported willingness to prescribe PrEP will be reported overall and for each independent variable. Descriptive statistics (median/interquartile ranges, frequencies/percentages) and comparisons between those willing to prescribe PrEP and not willing will be reported for each independent variable in bivariate logistic regressions. Multivariable logistic regression models will be performed adjusting each independent variable by a priori variables, such as age, race and sex, and other variables included based on literature review.

**Logistic regression analyses:** Bivariate models will be fit and variables with p-values  $\leq 0.1$  will be included in multivariable logistic regression analyses. Model fit will be determined using Hosmer and Lemeshow tests. A priori variables will be selected and included based on literature review.

**Sub-aim 2:** To further assess individual-level determinants, we will conduct focus groups with Black cis-gender women living in Alabama to explore desired PrEP educational materials and communication strategies from gynecologic care teams.

**Development of the Interview Guide.** We will develop a semi-structured focus group guide for focus groups in collaboration with our CAB, refining it through pilot testing (Table 1). The guide will ensure that appropriate lines of inquiry are pursued among participants by providing topical area questions and probes, while also encouraging explorations of participants' experiences and allowing for the emergence of novel concepts and ideas. The guide will include a mixture of descriptive/narrative questions (e.g., Tell me about experiences you or women you know have had *visiting gynecology clinics*) and questions structured around possible implementation strategy components guided by review of the literature (e.g., Tell me about your experiences discussing sexual health with your gynecologist) to facilitate a more granular understanding of : 1) Black cis-gender women's perceptions of informational content needed to motivate engagement in PrEP care, 2) who in the healthcare team would they feel comfortable discussing sexual health and HIV prevention with and 3) specific implementation strategy components for GYN clinics that would aid in engaging Black cis-gender women in PrEP care. (**Table 1.** Includes possible topics for focus groups)

**Sample:** Five focus groups, consisting of 5-6 people, will be conducted. Recruitment will be coordinated through flyers and direct referrals from UAB's GYN Continuity Clinic. Sessions will be conducted in private rooms located in public buildings or, if the ability to conduct in-person interviews is affected by the COVID-19 pandemic, focus groups will be conducted virtually to ensure the safety of participants as well as staff. *Inclusion criteria:* 1) self-reported HIV-negative status, 2) Black cis-gender women, 3) English speaking, 4) Age 18-45 years (this age range is based on current HIV epidemiology supporting greatest incidence in cis-gender women aged < 54).

**Procedures.** Potential participants who are referred will be asked to complete an online screening tool to determine whether they meet eligibility criteria and to collect demographic data. If participants are eligible, study staff will contact them via phone to schedule focus groups. Focus groups will be conducted in private, quiet, mutually convenient locations by study staff who are trained in qualitative methods and interview techniques. Informed consent will be obtained prior to each focus group and participants will receive \$50 in compensation upon completion. All focus groups will be digitally audio recorded, professionally transcribed, and de-identified.

**Qualitative Data Analysis.** See Qualitative analyses sub-Aim 1.

**Data Integration:** We will be integrating our qualitative and quantitative data findings through joint displays, bridging results using visual displays to connect major themes.

**Expected Outcomes:** Following evaluation of overall themes, findings from this aim will create an in-depth and granular understanding of key factors that are necessary to address in development and refinement of PrEP4Her, our implementation strategy to integrate PrEP services into routine GYN care. Large sampling of GYN providers will also allow for greater generalizability of our implementation strategy to other Southern sites.

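### The Aim 1 provider survey makes no allowance for providers who share a clinic and lists clinic name as an ordinary predictor, so uncertainty about clinic-level predictors is understated when respondents share clinics

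*Combined protocol and SAP*

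**What the plan says.** The survey is described in the protocol under Specific Aim 1, Sub-aim 1. Eligible respondents are "currently practicing gynecologists or advanced practitioners at GYN clinics", recruited one by one through referral from a state professional body and a university department. No limit per clinic is given. The primary outcome is willingness to prescribe PrEP, yes or no.

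The power paragraph states "We will administer our survey to 250 Alabama gynecologists" and continues: "This sample size will allow us to detect odds ratios of willingness to prescribe PrEP of 2.09" for an evenly split binary predictor and 1.47 per standard deviation of a continuous one, "assuming 80% power, 30% baseline percentage of willingness to prescribe PrEP" and a 5% type I error rate. With covariates the figures become 2.27 and 1.54.

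Table 2 places the predictors under a setting-level heading and sets the task "Determine denominator (i.e. number of providers in clinical settings) willing to prescribe PrEP". Its socio-demographic line reads "race/ethnicity, clinic name, gender, years of practice, clinic resources, characteristics of populations served", followed by knowledge, stigma and practice measures.

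The analysis is bivariate logistic regression, a screen at p ≤ 0.1, then multivariable logistic regression with some variables chosen in advance. There is no random effect, GEE, cluster-robust variance, ICC or design effect. The PrEP4Her Analysis Plan covers Aim 3 only and does not deal with this survey.

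**The concern.** Providers in one clinic share resources, leadership and patients, so their willingness to prescribe is likely to be correlated. A predictor that takes the same value for every provider in a clinic then carries less information than the number of respondents suggests. Ordinary logistic regression ignores this.

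The survey is meant to identify structural barriers and to inform state-wide implementation, so clinic-level predictors are among its targets. A chance association with clinic resources could be reported as a barrier or facilitator and carried into the choice of PrEP4Her components in Aim 2.

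Listing clinic name as a predictor raises a second problem. As a set of indicators it largely duplicates the other clinic-level measures, and any clinic whose respondents all answer alike is perfectly predicted.

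**Working it through.** **Inputs from the protocol:** N = 250, power 80%, type I error 5% (two-sided reproduces the figures; one-sided does not), 30% baseline willingness, 50/50 split for a binary predictor. **Not in the documents, so assumed:** respondents per clinic (m) and ICC.

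**Step 1. Reproduce the stated odds ratios.**

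- Continuous predictor: ln(OR) = (1.960 + 0.842) / √(N·p·(1−p)) = 2.802 / √(250 × 0.30 × 0.70) = 2.802 / 7.246 = 0.387, so OR = 1.472 (stated 1.47).
- Binary predictor at OR 2.09: the comparison proportion is 0.4286 × 2.09 / (1 + 0.4286 × 2.09) = 0.472. The pooled two-proportion formula for 0.30 against 0.472 needs 124 per group, 248 in all. Solving for the odds ratio at N = 250 gives 2.083 (stated 2.09).

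Both figures reproduce with 250 independent responses and no design effect.

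**Step 2. Apply a design effect to predictors shared within a clinic.** DEFF = 1 + (m − 1) × ICC and effective N = 250 / DEFF, put back into the Step 1 formulas. The sample size that restores the stated odds ratios is 250 × DEFF.

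| m | ICC | DEFF | Effective N | Detectable OR, binary / continuous | Power at OR 2.09 | N to restore |
|---|---|---|---|---|---|---|
| 1 | any | 1.00 | 250 | 2.08 / 1.47 | 80% | 250 |
| 2 | 0.05 | 1.05 | 238 | 2.12 / 1.49 | 78% | 263 |
| 5 | 0.05 | 1.20 | 208 | 2.23 / 1.53 | 73% | 300 |
| 5 | 0.10 | 1.40 | 179 | 2.37 / 1.58 | 66% | 350 |
| 10 | 0.10 | 1.90 | 132 | 2.73 / 1.70 | 53% | 475 |

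**Step 3. Simulate ordinary logistic regression with no true effect.** There were 3,000 runs per setting with equal clinic sizes and a clinic random intercept; Monte Carlo error near 5% is √(0.05 × 0.95 / 3000) = 0.4 percentage points. The SE ratio is the true standard error divided by the reported one.

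| m | ICC (latent scale) | Clinic-level predictor: type I error, SE ratio | Provider-level predictor: type I error, SE ratio | Clinics answering alike |
|---|---|---|---|---|
| 2 | 0.05 | 5.5%, 1.03 | 5.5%, 1.02 | 59% |
| 5 | 0.05 | 6.0%, 1.07 | 5.5%, 1.02 | 20% |
| 5 | 0.10 | 7.7%, 1.12 | 5.7%, 1.02 | 22% |
| 10 | 0.10 | 13.1%, 1.29 | 5.1%, 1.02 | 7% |

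The ICC here is set on the latent logistic scale, so it is smaller on the yes/no scale. At m = 5 and latent ICC 0.10, the SE ratio implies a design effect of 1.123² = 1.26, or an ICC of (1.26 − 1)/4 = 0.065. This is why the simulated 7.7% is below the 9.8% from 2 × [1 − Φ(1.96/√1.4)].

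A separate simulation of 50 clinics of five, with ICC 0.057 and 0.108, gave 6.7% and 9.3% for the ordinary analysis of a clinic-level predictor. Cluster-robust standard errors gave 4.4% to 4.7%.

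**Step 4. Clinic name as fixed indicators.** A clinic with uniform answers has no finite coefficient. The last column of the Step 3 table shows how often that happens; a clinic with a single respondent is always in this position. The indicators also leave little or no variation from which to estimate clinic resources or populations served.

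**The case against.** A reader might infer that all of the survey's standard errors are too small and that clinic-level effects cannot be estimated. The documents do not support either statement.

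- **Most listed predictors belong to the provider.** Race, gender, years of practice, knowledge, stigma and practice can differ between colleagues. The simulation finds the ordinary analysis about right for predictors that vary within a clinic, so 2.09 and 1.47 should stay for them. This stands.
- **The size cannot be read from the documents.** Working at a gynecology clinic is an eligibility condition, not a sampling stage, and no number of clinics is given. With one respondent per clinic nothing changes, and with two the change is small. This stands, and is why the size is given as a range.
- **The estimation problem is conditional.** The bivariate models do estimate effects of clinic resources. Trouble arises only if clinic name is kept after the screen or chosen in advance and then enters as indicators. Colleagues may also describe the same clinic differently, so collinearity is large rather than exact. This stands.
- **The two harms largely exclude each other.** Clinic indicators would absorb the between-clinic variation that makes the ordinary standard errors too small. This stands, but the plan handles neither case.
- **The survey is formative.** Its results are combined with interviews and focus groups and reviewed with the advisory board, which limits the damage from one false association. It does not justify reporting intervals that are too narrow when the variable needed to correct them is on the list.

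**Conclusion.** The point holds for predictors shared within a clinic. The plan has no method for within-clinic correlation, its detectable odds ratios assume 250 independent responses, and clinic name is listed in a role that does not suit it.

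For clinic-level predictors the understatement ranges from none (one respondent per clinic) through slight (2.12 / 1.49 at two per clinic, ICC 0.05) to material (2.73 / 1.70 at ten per clinic, ICC 0.10, where power at an odds ratio of 2.09 is 53%). These sizes rest on assumed, equal clinic sizes and assumed ICCs. Provider-level predictors are essentially unaffected. Collinearity and infinite estimates arise only if clinic name is fitted as fixed indicators, which the plan as written permits.

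**What to change.** 1. Remove clinic name from the predictor list in Table 2 and name it as the cluster identifier.
2. Fit the planned logistic models with cluster-robust (GEE-type) standard errors and a small-sample correction. With a working-independence structure the odds ratios are those of the planned models and only the standard errors change. A random intercept would instead give clinic-specific odds ratios and may be poorly identified if many clinics have one respondent.
3. Report the number of clinics, the distribution of respondents per clinic and the observed ICC.
4. Keep 2.09 and 1.47 as the unadjusted detectable odds ratios for provider-level predictors. For clinic-level predictors add, with the assumptions stated: 2.12 / 1.49 (two per clinic, ICC 0.05), 2.23 / 1.53 (five, 0.05), 2.37 / 1.58 (five, 0.10) and 2.73 / 1.70 (ten, 0.10), with no change at one per clinic.

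No new data are needed, and the analysis can be done this way even if responses are already in. The cost is some cleaning and matching of clinic names, and less favourable stated figures for clinic-level predictors. If clustering proves negligible, the results will barely move and the report will show why.
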